## Analysis Cohorts and Datasets

In the definitions below, a *cohort* refers to a particular set of participants and a *dataset* defines the time (or time intervals) contributed by participants in a cohort.

- **Screened cohort** – all participants with a screening CRF marked complete.
  - **Enrolled cohort** – subset of screened, who were eligible and enrolled i.e. received a study number
  - **Enrolled dataset** – analysis set of all baseline and follow-up data contributed by each participant in the enrolled cohort, regardless of compliance to group
- **Intervention cohort** – subset of enrolled cohort who are enrolled during an intervention time period
- **Control cohort** – subset of the enrolled cohort who were enrolled during the control block

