### Exposure and Outcome Definitions

#### Aim 1 exposure

- Allocation arm
  - Intervention block group for all eligible participants during that “on block” (regardless of actual monitoring receipt i.e., intention-to-treat).

#### Aim 1

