## Analyses

### Baseline Data

Recruitment will be described for screened cohort including reasons for ineligibility among those screened.

Enrollment & Demographics by arm will be described for enrolled cohort. Summary statistics (e.g., frequencies, percentages, means, medians, inter-quartile range, minima and maxima) that are appropriate to the measurement scale will be used to describe baseline demographic, obstetric and medical history per tables developed prior to first interim analysis of data. No formal statistical testing will be performed to compare distributions of baseline characteristics between groups.

**Commented [BAA2]:** Should we do this to assess group balance?

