### Participant Disposition and Retention

The numbers of participants screened, enrolled, and allocated to each arm will be tabulated. A flow diagram will be provided which presents the numbers and percentages of participants contributing to the Primary Evaluable cohort. For any participant excluded from the cohort, the diagram will provide reasons for exclusion.

NCT ID: 2019P000885

Document Date: September 26th 2021

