#### Protocol Deviations

Protocol deviations will be summarized in frequency tables

**Aim 1: To estimate the clinical effectiveness of wireless physiologic monitoring of women in the first 24 hours after cesarean delivery**

**Exposure** Intervention arm

**Primary outcome** Severe Maternal Outcome

**Endpoint** Discharge from hospital

**Descriptive statistics:** Proportion of women with one or more SMO, overall and by arm.

**Inferential statistics:** SMO will be statistically compared by arm using a Poisson model.

An intention to treat approach will be used to assess effectiveness. Thus, all women eligible for monitoring during an intervention arm including those who 1) declined consent 2) were missed from screening 3) were screened and not enrolled 4) enrolled but did not receive the intervention will be included in the intervention. The event rate for the primary and secondary outcomes will be calculated during the intervention and control time periods on all eligible women during those time periods. While intervention allocation was at the level of the two-week time period, the analysis will be at the individual patient level adjusting for clustering of observations within time periods. Using a logistic regression mixed effects model, with random effects to account for time block, we will compare the rate primary outcome between the intervention and control time periods.

Exploratory analyses will be used to determine if the intervention has a more significant effect in certain sub- groups of women (e.g. women <35, or women with more education). The interaction between study arm and comorbidities (i.e., HIV, hypertension, pulmonary, cardiac or kidney disease, malaria) will also be tested in logistic regression models. Subgroup effects will be reported if there is strong evidence of heterogeneity of intervention effect.

**Commented [BAA3]:** Intervention time periods will include women who  
-Declined consent  
-Were missed from screening  
-Were screened and unable to enroll  
-Enrolled but did not get the “full intervention”  
-Screened and enrolled – deceased before monitoring  
-Women ineligible due to language but those women will not be known in the control group.

**Commented [BAA4]:** Random effects for week using a mixed effects model  
Vs GEE where you put in clustering or correlation

**Commented [BAA5]:** Account for missing data in control period  
- impute for variables that are available and are independent for the intervention  

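### The SAP's primary analysis takes in all eligible women in each block, but no defined cohort contains them and no outcome source is stated for intervention-block women who are not enrolled

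*SAP*

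**What the plan says.** **Primary analysis (SAP).** Aim 1 exposure is set by block for every eligible woman, "regardless of actual monitoring receipt i.e., intention-to-treat". The Aim 1 inferential text puts into the intervention group "all women eligible for monitoring during an intervention arm including those who 1) declined consent 2) were missed from screening", together with women screened but not enrolled and women enrolled but not monitored. Event rates are to be calculated "on all eligible women during those time periods", for both period types.

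**Cohorts (SAP, Analysis Cohorts and Datasets).** The screened cohort is "all participants with a screening CRF marked complete". The enrolled cohort is the part of it that was eligible and has a study number. The intervention cohort is the "subset of enrolled cohort who are enrolled during an intervention time period", and the control cohort is its counterpart for control blocks.

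**Tables (SAP).** Under Baseline Data: "Demographics by arm will be described for enrolled cohort". Participant Disposition and Retention asks for a flow diagram of participants "contributing to the Primary Evaluable cohort", a term the text does not define.

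**Outcome collection (protocol).** Study Procedures item 11 has a research assistant review the charts of enrolled participants every 24 hours for SMOs, and also read the clinicians' daily ward reports. The Study Intervention section and the Study Population Overview table assign record review without consent to controls in non-intervention blocks.

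**Eligibility.** The protocol has one list of criteria for peripartum women. It requires willingness to wear the sensor and to stay on the ward, and it excludes women who speak neither study language. An SAP margin comment on who counts in intervention periods lists "Women ineligible due to language but those women will not be known in the control group".

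**The concern.** The stated principle is sound for an on/off block design: count every eligible woman according to the block she delivered in. The cohort definitions, the baseline table and the described outcome collection follow a narrower set, namely women who were screened and given a study number.

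Two things are at stake. First, an analysis dataset built from the cohort section would omit women whom the Aim 1 text requires. The baseline table, a main check on comparability in a non-randomised comparison, would then describe a different group from the primary analysis. Second, if SMOs are collected only for enrolled women in intervention blocks but for every emergency cesarean in control blocks (Study Procedures item 4), the arms could differ by selection.

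**Working it through.** **1. Each type of intervention-block woman, set against the documents.**

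| Eligible woman | In Aim 1 analysis | In screened cohort | In enrolled and intervention cohorts | SMO source stated |
|---|---|---|---|---|
| Enrolled, monitored | yes | yes | yes | charts and ward reports |
| Enrolled, not monitored | yes | yes | yes | charts and ward reports |
| Screened, declined or not enrolled | yes | yes | no | none |
| Missed from screening | yes | no | no | none |

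The last two rows are in the primary analysis but outside the intervention cohort. The last row is in no cohort at all.

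**2. Can the criteria be applied in both arms?** The written criteria are common to both. Willingness and language, however, are learned by speaking to the woman, and controls have record review only. Keeping decliners in the analysis removes part of the asymmetry in willingness, but it conflicts with the inclusion list, which requires consent and willingness. On language, the protocol expects more than 95% of the local population to speak a study language. With 112 cesareans per block, the women affected number fewer than 112 × 0.05 = 5.6 per block, or 112 × 13 × 0.05 = 72.8 per arm.

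**3. How many women have no stated outcome source?** Inputs from the protocol's Sample Size section: 8 to 10 emergency cesareans a day, about 112 per two-week block, 85% consent, 13 blocks per arm.

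- The plan's own figure: 112 × 0.85 = 95.2, rounded to 95 per block; 95 × 13 = 1,235. This reproduces the stated group size.
- All emergency cesareans in intervention blocks: 112 × 13 = 1,456.
- Not enrolled: 112 − 95 = 17 per block; 17 × 13 = 221; 221 / 1,456 = 15.2%.

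The figure moves with its inputs:

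- The 112 is a count of emergency cesareans, so eligibility exclusions lower the figure.
- The protocol calls 85% conservative against recruitment above 90% in earlier studies. At 90% the count is 112 × 0.10 × 13 = 145.6, and it is lower still above 90%.
- The 112 equals 8 a day × 14 days. At 10 a day and 85% consent the count is 140 × 0.15 × 13 = 273.
- The protocol plans to capture every woman and allows nothing for women missed from screening. Any such women would add to the count.

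**4. Bias.** This cannot be calculated. The documents give no SMO risk for women who decline or are missed.

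**The case against.** The strongest reply is that the primary analysis set is already stated. The Aim 1 text names the women to include, the exposure definition agrees, and nothing ties the SMO model to the cohort section. The enrolled cohort is used only for description. The SAP also defines eligibility for monitoring as meeting the criteria in a block allocated to monitoring, without requiring enrolment. This stands in part: a reader might infer that the primary population is undefined or is enrolled-only, and the documents do not support that. The defect is that no cohort, baseline table or flow diagram matches the stated population. The eligibility definition covers intervention blocks only, and the count that uses it is taken within the enrolled cohort.

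A reader might also infer that the eligibility rules differ by arm. They do not; what differs is whether they can be applied. The margin comment on language can be read as a proposal to treat the arms alike by including those women, but the body text has not adopted it.

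On outcomes, three points weaken any claim that data will not exist. The ward reports in item 11 are routine and may cover all women. The SAP's Data sources section lists chart review without limiting it to particular women. And the SAP places controls, who give no consent, in its enrolled cohort, so enrolled need not mean consented. None of these passages says that non-enrolled intervention-block women are covered, and the waiver request is worded for controls. Consent pages and the chart-review appendix are not available here. This part is therefore a gap in what is stated and not proof of missing data.

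Finally, a reader might infer a bias in favour of monitoring. The documents do not support a direction. The Aim 1 text does not plan to compare enrolled intervention women with all controls, and the consent section lets incapacitated women enter without prior consent. The Sample Size section also plans 1,235 controls, the same number as in the intervention group, so it is not settled that every control-block cesarean would be reviewed.

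**Conclusion.** The concern holds as an internal inconsistency that should be fixed. The primary population in the Aim 1 text has no matching cohort, the baseline table describes a narrower set, and the cohort named for the flow diagram is undefined. These points can be read directly from the SAP.

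The outcome-source part is less certain. On the protocol's volume and consent share, about 17 women per intervention block (221 of 1,456, or 15%, before eligibility exclusions) could be counted in the analysis without a stated source for their outcome. That rests on 112 cesareans per block, 85% enrolment, and no approval or procedure in the pages not seen. Severity rests on the mismatch in the text and not on any estimate of bias.

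**What to change.** **SAP.** In Analysis Cohorts and Datasets, add a primary intention-to-treat cohort defined identically in both arms from criteria readable in the records:

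- age, with the limit reconciled between the protocol (over 18 in the inclusion table) and the SAP (18 and older);
- emergency cesarean at the study hospital;
- not admitted directly to ICU;
- arm set by the block at delivery.

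Identify the women from one source used alike in both block types, such as the theatre log books that the protocol names as a RE-AIM data source. State that consent, willingness, language and device allergy govern receipt of monitoring and not membership of this cohort. Point Baseline Data, Participant Disposition and Retention and the Aim 1 model to it. Define or delete the Primary Evaluable cohort, and resolve the margin comment on who is included.

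**Protocol.** In the Study Intervention section and Study Procedures item 11, state that the same SMO review (charts and 24-hour reports) covers this cohort in both block types, subject to IRB approval of a waiver for non-enrolled women if it is not already held. State also whether record review continues when a woman enrolled without consent later declines. The consent section now says that all study procedures stop, and chart review is one of them.

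**If approval is refused.** Report the number without outcomes by arm, and do not label the enrolled-only comparison intention-to-treat. Otherwise keep that comparison as a sensitivity analysis.

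**Cost.** SAP wording, one IRB amendment if approval is not already held, and about 221 extra chart reviews on the planning figures before exclusions (273 at 10 cesareans a day). The IRB may refuse for women who declined.

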## Interim Monitoring

The DSMB will be responsible for review of operational and endpoint to assess the relative safety and relative effects of the interventions during the trial and monitor the overall conduct of the clinical trial.

The DSMB will provide recommendations about stopping or continuing the trial. The timing of formal interim analyses is yet to be determined. No formal stopping rules have been established.

## Analyses

### Baseline Data

Recruitment will be described for screened cohort including reasons for ineligibility among those screened.

Enrollment & Demographics by arm will be described for enrolled cohort. Summary statistics (e.g., frequencies, percentages, means, medians, inter-quartile range, minima and maxima) that are appropriate to the measurement scale will be used to describe baseline demographic, obstetric and medical history per tables developed prior to first interim analysis of data. No formal statistical testing will be performed to compare distributions of baseline characteristics between groups.

**Commented [BAA2]:** Should we do this to assess group balance?

### Participant Disposition and Retention

The numbers of participants screened, enrolled, and allocated to each arm will be tabulated. A flow diagram will be provided which presents the numbers and percentages of participants contributing to the Primary Evaluable cohort. For any participant excluded from the cohort, the diagram will provide reasons for exclusion.

NCT ID: 2019P000885

Document Date: September 26th 2021

#### Intervention: Monitoring Use and Monitoring Interruptions.

Numbers of participants in the enrolled cohort who are eligible for wireless monitoring and receiving monitoring will be described. Numbers of participants with monitoring interruptions

- “Eligible for Monitoring” is defined as meeting criteria and with an allocated block for monitoring.
- “Receiving Monitoring” defined as using a current health device and having wireless vital sign monitoring data transmitted.
- “Time on intervention” calculated from reported monitoring start time to monitoring end time
- “Monitoring interruptions” - Percent of participants with monitoring interruption will be calculated out of those who received monitoring – defined as those who > 6 hours without monitoring data during the time on intervention.

#### Protocol Deviations

Protocol deviations will be summarized in frequency tables

**Aim 1: To estimate the clinical effectiveness of wireless physiologic monitoring of women in the first 24 hours after cesarean delivery**

**Exposure** Intervention arm

**Primary outcome** Severe Maternal Outcome

**Endpoint** Discharge from hospital

**Descriptive statistics:** Proportion of women with one or more SMO, overall and by arm.

**Inferential statistics:** SMO will be statistically compared by arm using a Poisson model.

An intention to treat approach will be used to assess effectiveness. Thus, all women eligible for monitoring during an intervention arm including those who 1) declined consent 2) were missed from screening 3) were screened and not enrolled 4) enrolled but did not receive the intervention will be included in the intervention. The event rate for the primary and secondary outcomes will be calculated during the intervention and control time periods on all eligible women during those time periods. While intervention allocation was at the level of the two-week time period, the analysis will be at the individual patient level adjusting for clustering of observations within time periods. Using a logistic regression mixed effects model, with random effects to account for time block, we will compare the rate primary outcome between the intervention and control time periods.

Exploratory analyses will be used to determine if the intervention has a more significant effect in certain sub- groups of women (e.g. women <35, or women with more education). The interaction between study arm and comorbidities (i.e., HIV, hypertension, pulmonary, cardiac or kidney disease, malaria) will also be tested in logistic regression models. Subgroup effects will be reported if there is strong evidence of heterogeneity of intervention effect.

**Commented [BAA3]:** Intervention time periods will include women who  
-Declined consent  
-Were missed from screening  
-Were screened and unable to enroll  
-Enrolled but did not get the “full intervention”  
-Screened and enrolled – deceased before monitoring  
-Women ineligible due to language but those women will not be known in the control group.

**Commented [BAA4]:** Random effects for week using a mixed effects model  
Vs GEE where you put in clustering or correlation

**Commented [BAA5]:** Account for missing data in control period  
- impute for variables that are available and are independent for the intervention  
- Use information from other people with the same arm  
- Create a missing category and use that as one the variable  
- Control for variables that are available in the chart

NCT ID: 2019P000885

Document Date: September 26th 2021

**Aim 2: To evaluate the clinical adoption of wireless physiologic monitoring in a RLS using an implementation science approach using the RE-AIM Implementation framework**

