Research assistants will be asked to document field notes at the time of consent to capture information on the length of time taken for the consent, if the participant had others present, and observations during the process of the consent (e.g. discussion by the participant with an attendant or family member)

If women are unconscious or in a mental state where they are unable to consent for themselves, an attendant or guardian will be approached for consent. As women in this condition are at high risk for morbidity and/or mortality inclusion in this study is key to achieve the objectives of reducing this risk. Additionally, women in this condition are the most likely to gain direct benefit from vital sign monitoring. As such if an attendant is not available the woman will be enrolled without consent to enable monitoring to begin immediately. Consent will be sought as soon as possible after the woman regains capacity to consent or an attendant becomes available. If the woman and/or her attendant declines to participate at that time all study procedures will be discontinued.

Study Procedures

1. A group meeting detailing the study background, procedures, risks and benefits will be held for all clinical providers in the department prior to study initiation.
2. We will obtain informed consent for clinicians and peripartum women admitted for delivery as described above.
3. A 2-hour training session on the use of the wireless monitoring system, nature of alerts and emergency mobile phone will be held for enrolled clinicians at a time convenient to them.
4. Alternative two-week blocks will be assigned to “intervention” vs “control”. During an “intervention block” all women delivering by emergency cesarean and consenting to participate will be monitored using the wireless device for the first 24 hours after delivery. During a “control

block" standard of care for monitoring will be used and women delivering via emergency cesarean will have record review only.

5. Maternity ward coverage schedules for enrolled specialist and midwives will be obtained. This will be used to determine the clinicians on call during each intervention block.
6. During the intervention block, midwives present in the theatre will be asked to perform the following tasks for any emergency cesarean deliveries s/he is present for:
 - a. Placement of the biosensor on any enrolled women s/he delivers by emergency cesarean delivery immediately after completion of the surgery.

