Aim 1: The primary outcome measure is the rate of severe maternal outcome (SMO). This is a composite measure drawn from WHO near miss morbidity criteria (Table 2). Secondary outcome measures include: the maternal mortality rate, maternal near miss rate and case fatality rates for postpartum hemorrhage, hypertensive disease and sepsis – the three most common causes of maternal death. The event rates for both primary and secondary outcomes will be compared using logistic regression models with the Generalized Estimating Equations approach to take into account of patients within clustering (due to time blocks). Exploratory analyses will be used to determine if a) the intervention is more powerful in certain subgroups of women and b) if any provider was consistently different in maternal outcomes regardless of intervention. The interaction between study arm and comorbidities (HIV, hypertension, pulmonary, cardiac or kidney disease, malaria) or provider will be tested in the logistic regression models. Subgroup effects will be reported if there is strong evidence of heterogeneity of intervention effect

Aim 2: We will apply the RE-AIM model to conduct a quantitative evaluation of the implementation of the intervention used in Aim. Table 4 describes the primary metrics to be measured and data sources from which it will be collected.

RE-AIM Implementation Science Framework ^{37,38}			
Metric	Dimension	Study Measure	Data source
Reach	Proportion of target population that participated in the intervention	
 Percent of women with successful placement of biosensor after delivery Total length of time for monitoring over 24hrs postpartum Percent of women participating in monitoring for 24 hrs 	
 Physiologic data from biosensor Time of delivery from chart records & theatre log books
Efficacy	Success rate if implemented as in guidelines	
 Percent of women with HR, BP, RR and Tp available at least every 4 hours for 24 hrs after delivery Percent of appropriate SMS alerts sent 	
 Physiologic data from biosensor RA review of mobile phones for SMS alerts and time of receipt

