## Study Objectives and Summary

Protocol title:	Wireless Physiologic Monitoring Among Postpartum Women
Design:	Single site, prospective pragmatic type 2 hybrid effectiveness-implementation trial utilizing a quasi-experimental, interrupted time series with repeated on/off periods
Study arms:	Repeated on/off intervention-control periods in 2-week blocks. Intervention group to receive wireless monitoring, and Control group to receive standard of care.
Population:	Women aged 18 and older undergoing emergency cesarean delivery at MRRH
Sample size:	Approximately 1266 women (633 per arm); dependent on clinical volume during blocks
Study sites:	Mbarara Regional Referral Hospital, Mbarara
Aim 1:	To estimate the clinical effectiveness of wireless physiologic monitoring of women in the first 24 hours after cesarean delivery at a referral hospital in a RLS.
Aim 2:	To evaluate the clinical adoption of wireless physiologic monitoring in a RLS using an implementation science approach using the RE-AIM Implementation framework.
Aim 3:	To use qualitative methods to explore clinical adoption by doctors and acceptability of wireless physiologic monitoring among postpartum women in RLS and understand facilitators and barriers to uptake of wireless physiologic monitoring.

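### The primary SMO comparison is assigned three different models (Poisson, logistic mixed, logistic GEE); none is ranked as primary and no effect measure is stated

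*SAP*

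**What the plan says.** Three passages of current text assign a model to the same comparison.

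- SAP, Aim 1, Inferential statistics, opening sentence: "SMO will be statistically compared by arm using a Poisson model". It gives no link function, variance estimator or cluster term.
- SAP, Aim 1, next paragraph, on the primary outcome: "Using a logistic regression mixed effects model, with random effects to account for time block". Just before this the SAP notes, in the past tense, that arms were allocated by two-week block, and it sets the level of the analysis: "the analysis will be at the individual patient level adjusting for clustering of observations within time periods".
- Protocol, Biostatistical Analysis, Aim 1, on primary and secondary outcomes: "logistic regression models with the Generalized Estimating Equations approach to take into account of patients within clustering (due to time blocks".

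The fourth margin comment in the SAP, beside the Aim 1 analysis, lists a mixed model with random effects for week and then the alternative: "Vs GEE where you put in clustering or correlation". It does not mention Poisson.

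The SAP's design row describes a "quasi-experimental, interrupted time series with repeated on/off periods". The protocol (Study Procedures, item 4) alternates intervention and control in two-week blocks, and its Sample Size section plans 13 blocks of each kind. The SAP sets a two-sided 0.05 level for the primary analysis.

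Neither document ranks the models, says that the SAP replaces the protocol on this point, or names an effect measure. Neither mentions degrees of freedom, a t or F reference, a corrected sandwich variance or a permutation test.

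**The concern.** The three models estimate different quantities. A Poisson model with log link gives a risk ratio, a logistic mixed model gives an odds ratio conditional on block, and logistic GEE gives a marginal odds ratio. Two analysts following the same documents could each report a different primary estimate and p-value, and each could say that the plan was followed.

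This concerns the single primary outcome of Aim 1. The SAP also speaks of allocation in the past tense, so blocks may already have begun. A model choice that is still open at that stage could be made after outcome data by arm have been seen.

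**Working it through.** **Inputs.** From the protocol's Sample Size section: 13+13 blocks, 95 consenting women per block (about 112 emergency cesareans × 85%), 1,235 per arm, ICC 0.01, 13% SMO, 5.7-point difference, 80% power, two-sided 0.05. From the SAP: about 1,266 women, which over the protocol's 26 blocks is 1,266/26 ≈ 49 per block. The SAP itself gives no block count. The 112 per block is relevant because the SAP's intention-to-treat analysis counts all eligible women, consenting or not.

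**The plan's own figures.** 1,235/(1 + 95 × 0.01) = 633, as stated; the usual 1,235/(1 + 94 × 0.01) gives 637. At 633 per arm, power for 5.7 points is 79.4% for 13% versus 18.7% and 92.0% for 13% versus 7.3%. The stated figures therefore reproduce, most closely as an increase.

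**Effect measures for 13% to 7.3%.**
- Risk ratio: 0.073/0.13 = 0.56.
- Marginal odds ratio: (0.073/0.927)/(0.13/0.87) = 0.0787/0.1494 = 0.53.
- Block-conditional odds ratio: 0.52. The block SD on the logit scale is √[0.01/(0.13 × 0.87)] = 0.297.

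**Poisson sentence followed alone.** A plain Poisson model takes the variance of a log rate as 1/(np). With binary outcomes in blocks of m it is (1−p)·DE/(np), where DE = 1 + (m−1)·ICC. The true standard error is therefore √[(1−p)·DE] times the reported one, and the type I error is 2·[1 − Φ(1.96/√((1−p)·DE))].

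| Women per block | ICC | DE | (1−p)·DE | 1.96/√ | Type I error | Simulated |
|---|---|---|---|---|---|---|
| 49 | 0.01 | 1.48 | 1.288 | 1.73 | 8.4% | 8.3% |
| 95 | 0.01 | 1.94 | 1.688 | 1.51 | 13.1% | 13.1% |
| 112 | 0.01 | 2.11 | 1.836 | 1.45 | 14.8% | 14.8% |
| 95 | 0 | 1.00 | 0.870 | 2.10 | 3.6% | 3.6% |

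The simulations used 13+13 independent beta-binomial blocks at 13% SMO, with 200,000 null runs. With no clustering the same model errs the other way, because Poisson variance overstates binomial variance.

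**Do the verdicts differ?** At 95 per block:
- Logistic mixed versus logistic GEE, both by z test: 0.8% of null runs.
- Unclustered Poisson versus the mixed model on t(24): 7.4% of null runs (12,000 runs) and 5.4% when the true change is 13% to 7.3% (6,000 runs).

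**Small-sample method.** With 26 blocks and two arms, 24 degrees of freedom remain, and the critical value is 2.06 instead of 1.96. If an uncorrected z test were used (an assumption), simulated type I error would be 7.2% for GEE and 7.1% for the mixed model. On t(24) it is 5.0% for GEE with variance multiplied by 13/12, and 5.8% for the mixed model.

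**The case against.** The strongest reply is that the SAP already requires adjustment for clustering within time periods, two sentences after the Poisson sentence. On a fair reading any model would be adjusted for block, and the block-adjusted models hardly differ. That largely stands. It removes the inference that the plan as written tests at 13%: this figure needs the Poisson sentence to be read against the rest of its own section, and at the SAP's stated size it is about 8%. What remains is that the models are unranked and the choice between risk ratio and odds ratio is open.

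A reader might also infer that the cluster unit is unsettled, because a margin comment says week. The body of the SAP and the protocol both use the two-week block, and the comment may be shorthand. The comment is weak evidence in any case, since the body text already adopts one of its two options.

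Finally, a reader might infer that the plan commits to a z test with about 7% error. The documents specify no reference distribution. This is a silence, not a contradiction, and deserves lower severity.

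**Conclusion.** The contradiction is real and should be resolved before outcome data by arm are analysed. Three models for one primary outcome stand in current text, unranked, with no effect measure. The direct consequence is an estimate that could be reported as a risk ratio of about 0.56 or an odds ratio of about 0.52 to 0.53 for the same change, with an unfixed p-value.

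Between the SAP's mixed model and the protocol's GEE the practical difference is small. A material loss of error control arises only if the Poisson sentence is followed without a cluster adjustment: about 8% to 15% across 49 to 112 women per block at ICC 0.01, and about 3.5% at ICC 0.

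These figures assume equal, independent blocks and no time trend. The documents give no correlation between successive blocks.

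The missing small-sample method is a secondary point, worth about 7% instead of 5% if a z test were used.

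**What to change.** In both documents:

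- Name one primary model, either the SAP's logistic mixed model or the protocol's logistic GEE, with its effect measure and the two-week block as the cluster.
- Label the other logistic model as a sensitivity analysis.
- Delete the Poisson sentence, or make it a sensitivity analysis with block-robust variance that reports the risk ratio.
- Resolve and remove the margin comment, confirming the two-week block.
- Record whether outcome data by arm had been seen when the choice was made.

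Secondary recommendation: state a small-sample method, for example t on the number of blocks minus 2 degrees of freedom (24 for 26 blocks), plus a bias-corrected sandwich variance if GEE is chosen.

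The cost is SAP wording and a protocol amendment, which concerns the review bodies in Uganda and the United States. No new data are needed. The small-sample method widens the interval slightly. Simulated GEE power falls from 93% to 90% for 13% to 7.3%, and from 81% to 76% for 13% to 18.7%; mixed-model power falls from 93% to 92% for 13% to 7.3%. Part of that loss is excess type I error being removed.
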